9.4. Data Sources

The information that allows to evaluate the primary and secondary objectives of this study will be collected by means electronic case report forms (e-CRFs). Only the investigator and his/her staff can access to this system and enter patient data. Other objectives such as Health related Quality of live assess though PROs, will be collected electronically, using a tablet.

The EORTC QLQ-C30 contains 30 items that cover health issues relevant to a wide range of cancer patients, 24 of which are aggregated into multi-item scales measuring functioning, symptoms (fatigue, pain, and nausea/vomiting), and global health and quality of life (QoL). The remaining six single items evaluate additional cancer-associated symptoms and the perceived economic impact of the disease and treatment ¹⁶. The QLQ-LC13 is a supplementary, lung cancer specific questionnaire with 13 items addressing symptoms associated with lung cancer and its standard treatment¹⁷. Regarding EORTC QLQ-C30, Cocks et al, performed qualitative interview results from 113 patients with cancer from Europe and the US and showed that concepts included in the QLQ-C30 are widely understood across language versions, and that existing items are relevant to patients across cancer types and disease stages. In this study sample, the 13 most frequently, spontaneously elicited concepts were already covered by the QLQ-C30 conceptual framework. As a conclusion of this assessment, the QLQ-C30 demonstrates good evidence of content validity for the assessment of functional health, symptom burden and health-related quality of life in patients with localised-to-advanced cancer¹⁸. Bergam et al¹⁷, considers that the results from international field testing lend support to the EORTC QLQ-LC13 as a clinically valid and useful tool for assessing disease- and treatment-specific symptoms in lung cancer patients participating in clinical trials, when combined with the EORTC core quality of life questionnaire.

Regarding PRO-CTCAE questionnaire validity, Dueck et al carried out an assessment with a total of 975 adults with cancer undergoing outpatient chemotherapy and/or radiation therapy enrolled in this questionnaire-based study between January 2011 and February 2012. A total of 940 of 975 (96.4%) and 852 of 940 (90.6%) participants completed PRO-CTCAE items at visits 1 and 2, respectively. At least 1 symptom was reported by 938 of 940 (99.8%) participants. All PRO-CTCAE items had at least 1 correlation in the expected direction with a QLQ-C30 scale (111 of 124, P < .05 for all). Stronger correlations were seen between PRO-

CTCAE items and conceptually related QLQ-C30 domains. Scores for 94 of 124 PRO-CTCAE items were higher in the ECOG PS 2 to 4 vs 0 to 1 group (58 of 124, P < .05 for all). Overall, 119 of 124 items met at least 1 construct validity criterion. Test-retest reliability was 0.7 or greater for 36 of 49 prespecified items (median [range] intraclass correlation coefficient, 0.76 [0.53-.96]). Correlations between PRO-CTCAE item changes and corresponding QLQ-C30 scale changes were statistically significant for 27 prespecified items (median [range] r = 0.43 [0.10-.56]; all $P \le .006$)¹⁹.

Our study will only assess the items related to CNS AEs with PRO-CTCAE.

The research center will be identified with a code, each patient included by this researcher will be identified by a unique number, so that in the central database each patient will be identified by a code of research center and patient number, which in no case will include data that allow identification.

The table that relates the personal data of the patients participating in the study and the identification code assigned to it will be kept only in the investigator's study file of the center and will only be accessible to the research team. In case of inspection by the competent health authorities or internal audit of the sponsor, the inspectors and / or auditors may access to the registry to verify the veracity of the data collected in the study, prior authorization of the IEC/IRB of the center.

Personal data will be treated in accordance with all applicable regulations: according to the Regulation (EU) 2016/679 of the European Parliament and the Council of April 27th, 2016 on Data Protection (GDPR). In Spain, it is regulated by the Organic Law 3/2018, 5th of December, on Personal data protection and digital rights guarantee.

9.5. Study Size

In the CROWN trial, the incidence of CNS AEs was 42%⁴ and we assumed that the incidence could be higher in the real clinical practice, but it is under detected as most cases are grade 1. We estimated that we need 116 ALK+ NSCLC patients with an 80% power to detect an incidence of 55% any grade CNS AEs using a 2-sided test. We expect that the recruitment will be completed over a period of one and a half years, as described in the study schedule at 20 sites countrywide.

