At a median of follow up of 60.2 months⁴ (95% CI, 57.4 to 61.6) in the lorlatinib group and 55.1 months (95% CI, 36.8 to 62.5) in the crizotinib group. The HR for PFS or death with lorlatinib versus crizotinib was 0.19 (95% CI, 0.13 to 0.27). Median PFS was NR (95% CI, 64.3 to NR) with lorlatinib and 9.1 months (95% CI, 7.4 to 10.9) with crizotinib. The 4- and 5-year PFS was 63% and 60% (95% CI, 51 to 68) with lorlatinib, respectively, and 10% and 8% (95% CI, 3 to 14) with crizotinib. Among patients with baseline brain metastases (measurable and/or non-measurable; n = 35 in the lorlatinib group and n = 38 in the crizotinib group), the HR for PFS or death with lorlatinib versus crizotinib was 0.08 (95% CI, 0.04 to 0.19); median PFS was NR (95% CI, 32.9 to NR) with lorlatinib and 6.0 months (95% CI, 3.7 to 7.6) with crizotinib. Five-year PFS was 53% (95% CI, 35 to 68) with lorlatinib and not evaluable with crizotinib as all patients had progression or death or were censored within 2 years. Among patients without baseline brain metastases, the HR for PFS or death with lorlatinib versus crizotinib was 0.24 (95% CI 0.16 to 0.36); median PFS was NR (95% CI, 64.3 to NR) with lorlatinib and 10.8 months (95% CI, 9.0 to 12.8) with crizotinib. Five-year PFS was 63% (95% CI, 52 to 71) with lorlatinib and 10% (95% CI, 5 to 18) with crizotinib.

Regarding the safety profile of the drug, the median treatment duration was 57.0 months (IQR, 13.9-63.3) with lorlatinib and 9.6 months (IQR, 4.7-17.1) with crizotinib. Overall, 49 of 149 patients (33%) treated with lorlatinib and 36 of 142 (25%) treated with crizotinib had at least one dose reduction. The median relative dose intensity was 99% (IQR, 80-100) with lorlatinib and 99% (IQR, 91-100) with crizotinib. All-causality any-grade AEs occurred in all patients in the lorlatinib group and in 140 of 142 patients (99%) in the crizotinib group; grade 3/4 AEs occurred in 77% and 57% of patients, respectively. A higher rate of grade 3/4 AEs from any cause in the lorlatinib group compared to the crizotinib group was mostly due to hypertriglyceridemia (25% v 0%), hypercholesterolemia (21% v 0%), weight gain (23% v 2%), and hypertension (12% v 1) with lorlatinib, 23% of patients had dose reduction, 62% had temporary treatment interruption, and 11% had permanent discontinuation because of AEs from any cause. Treatment-related AEs caused

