permanent treatment interruption in eight patients (5%), which happened in the first 26 months. With crizotinib, 15% of patients had dose reduction, 48% had temporary treatment interruption, and 11% had permanent discontinuation because of AEs from any cause.

Solomon et al reported lorlatinib is associated with neurologic toxicity (mood/speech and cognitive areas), accounting for 35% of patients in the CROWN trial (3yr follow up of the pivotal trial⁸), being in most patients grade 1. CNS AEs did not have a negative impact on patient-reported quality of life. Most CNS AEs resolved (33% without intervention and 17% with lorlatinib dose modification), while 38% were unresolved; most required no intervention. Lorlatinib dose modification did not influence PFS. Few observational studies have reported the frequency of CNS toxicity on patients with ALK+ NSCLC receiving lorlatinib, however no information is available regarding patients from South Europe. The study will be relevant to learn more about the frequency in our population and about the clinical management in real clinical practice.

Lorlatinib also had a manageable safety profile, with hyperlipidemia, weight gain, and hypertension being the most common G3/4 adverse events and some others with lower frequency as the alterations at the CNS level (mood/speech and cognitive) that generate some uncertainties regarding an adequate management. Occurrence of adverse events with lorlatinib in Spain (2nd and later lines approval in February 2021) is known in later lines of treatment and it seems that several factors involved in that previously treated population (use of radiotherapy, presence/absence of baseline intracranial metastasis, use of concomitant drugs, personal clinical history of psychiatric/mood diseases, etc.) are associated to certain types of AEs, i.e. the CNS adverse events⁶, but the occurrence of those AEs are not well-known with the use of the drug in the first line of treatment (local approval February 2023) and that is one of the reasons why this data gap with lorlatinib should be covered.

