9.7. Data Analysis

General Considerations

The analysis plan will be fully described in a written and approved statistical analysis plan (SAP). The SAP will describe all statistical analyses, including definition of study outcomes and scoring of the different scales, and will further provide a detailed description of analyses to be performed and describe methods to deal with missing data and censoring. The final SAP will include the tables shell to be used for the final data analyses. Moreover, an interim analysis(es) to characterize dropouts and collecting only critical data elements (ie, variables aligned with the study objectives) to minimize site/participant burden will be conducted.

Descriptive analyses will be carried out to evaluate the objectives of the study. In order to describe the profile of the patients under study, a descriptive statistical analysis of each and every one of the variables included in the notebook will be carried out for this purpose.

Categorical variables are described by their absolute and relative frequency. Continuous variables are described with total n, valid n, n unavailable, means, standard deviation, quartiles, minimum and maximum. Progression-free survival will be measured from treatment initiation to evidence of tumor progression or death. Overall survival will be measured from treatment initiation to death. Patients will be censored at last control, if are lost during the follow-up.

The safety assessment will be based primarily on the frequency and severity of AE. AE will be summarized by presenting the number and percentage of these figures in the total number of patients. The absolute and variable frequencies of each AE with respect to the total number of reported AEs will also be presented. If applicable, the codification of the Medical Dictionary for Regulatory Activities (MedDRA)) will be useful Medication will be coded using WHO Drug Dictionary.

Survival analysis will be performed using Kaplan Meier method. A Cox regression model will be carried out to find independent variables associated with overall survival or time until disease progression.

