9.9. Limitations of the Research Methods

This is a non-interventional study in clinical practice. Study results might not reflect pivotal clinical trial results, in which patients are assigned to active or control group by chance (through randomization) to reduce errors or bias.

Additionally, our study population exhibits a low incidence of NSCLC patients, approximately 3-4%. Consequently, the current study is descriptive in nature, as it lacks the statistical robustness (relatively small sample, but almost similar to the total of patients included in the pivotal trial) necessary to establish a significant association between a specific adverse event and the drug. The medical literature contains analogous examples of post-authorization safety studies that offer valuable information²⁰⁻²² required by physicians and, in our case, considering that lorlatinib has become the first TKI and biomarker targeted therapy providing the longest efficacy (mPFS not reach after 60.2 months of follow-up in its pivotal trial) reported for all the solid tumors to date⁴.

Data collected in this study will reflect clinical practice in Spain. As a result, they may not be generalizable to studies conducted elsewhere, due to differences in clinical practice and patient characteristics.

The study is limited to a data collection and does not generate any risk or benefit to the patient. However, this study will allow progress in the knowledge of the conditions and factors associated with the use of lorlatinib.

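### The 116 patients are justified by power for a test against 42% that section 9.7 does not plan, and the 42% comes from much longer follow-up than this study will have

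*Protocol*

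**What the plan says.** **Sample size.** Section 9.5 takes as reference that in CROWN "the incidence of CNS AEs was 42%⁴", expects a higher rate in routine practice, and concludes that the study will "need 116 ALK+ NSCLC patients with an 80% power to detect an incidence of 55% any grade CNS AEs using a 2-sided test". The abstract and sections 9.1 and 9.2 repeat this. No alpha, null hypothesis or time window is given.

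**Analysis.** Section 9.7 evaluates the objectives descriptively. For safety, "AE will be summarized by presenting the number and percentage of these figures in the total number of patients". The only modelling it names is Kaplan-Meier and Cox regression, the latter for overall survival and progression. Section 9.9 says that "the current study is descriptive in nature, as it lacks the statistical robustness" needed to show a significant link between a particular adverse event and the drug; section 9.1 says the same, and the abstract also calls the study descriptive.

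**Benchmark.** Reference 4, the source of the 42%, is the 5-year CROWN report. Section 7 gives a median follow-up of 60.2 months for its lorlatinib group and says that "the median treatment duration was 57.0 months (IQR, 13.9-63.3) with lorlatinib". For the same trial at 3 years, section 7 describes neurologic toxicity "accounting for 35% of patients in the CROWN trial".

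**Observation here.** Recruitment runs from 1 June 2025 to 30 November 2026, and data collection ends on 30 November 2027 (abstract and section 6).

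**The concern.** There are two separate problems.

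First, a power statement describes a test. If no test is planned, it tells the reader nothing about what 116 patients will deliver. The useful property of a descriptive safety study is how precisely it estimates the incidence, and the protocol does not give that.

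Second, the proportion of patients who have ever had a CNS event can only stay level or rise as follow-up lengthens. Setting a crude percentage from 12 to 30 months beside a 5-year figure is not a like-for-like comparison. An observed rate near or below 42% could reflect a shorter window rather than a lower risk. This touches the event of special interest in the primary objective.

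**Working it through.** **Step 1. Reproduce the 116.** Inputs from section 9.5: p0 = 0.42, p1 = 0.55, power 80%, two-sided. Assumed: alpha 0.05.

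- One-sample test, null and alternative variances: n = [(1.96·√(0.42·0.58) + 0.8416·√(0.55·0.45)) / 0.13]² = [(0.967 + 0.419)/0.13]² = 113.7, so 114.
- Alternative variance only: (1.96 + 0.8416)²·0.2475/0.13² = 114.9, so 115.
- Arcsine formula: 115.3, so 116, the stated figure.
- One-sided versions give 90 to 98, and a two-sample comparison 231 per group. Neither fits.

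Power at n = 116:

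- Normal approximation: z = (0.13·√116 − 0.967)/0.497 = 0.87, which gives 80.8%.
- Exact binomial (reject at 60 or more, or at 37 or fewer; actual alpha 0.038): 78.9%.

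The stated size is therefore correct for a one-sample two-sided test against a fixed 42%.

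**Step 2. Look for that test.** Section 9.5 needs a null of 42%, an alpha and a rejection rule. Section 9.7 gives adverse events a count and a percentage, with no comparison with 42%. Its Cox model concerns other outcomes. The sample size and the analysis do not match.

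**Step 3. Compare the windows.**

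| | CNS rate | Observation |
|---|---|---|
| CROWN, 5-year report | 42% | median follow-up 60.2 months; median treatment 57.0 months (IQR 13.9–63.3) |
| CROWN, 3-year report | 35% | 3 years |
| This study | 55% assumed | 12 months (last patient enrolled) to 30 months (first) |

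The last row runs from enrolment to 30 November 2027. Patients enrol 7 to 28 days after their first dose, so time from first dose is longer by at most four weeks.

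Eighteen months of potential observation requires entry by about 30 May 2026, which is 12 months into an 18-month recruitment period. If recruitment were even (an assumption), that is 12/18, or about 77 of 116 patients. A crude percentage counts the other third as fully observed.

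**Step 4. What 116 patients deliver.** Half-width of a 95% CI = 1.96·√(p(1−p)/116):

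- p = 0.42: 9.0 percentage points.
- p = 0.55: 9.1 percentage points.

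Exact interval for 64/116 (55.2%): 45.7% to 64.4%.

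**The case against.** **The design is ordinary and the number is right.** Testing a single cohort against a fixed historical rate is common, and step 1 shows that 116 fits it. This stands: there is no arithmetic error.

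**Detail may be in the SAP.** Section 9.7 defers detailed methods, so a test could appear there. That explains a missing formula. It does not remove the conflict, because the protocol itself fixes both the power claim and a descriptive analysis. Cumulative incidence and confidence intervals are commonly SAP content, so their absence is not the fault raised here; they are offered as part of the repair.

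**The follow-up gap may be small.** The documents give no onset times. If CNS events come early, most would fall within 12 months. A quarter of CROWN lorlatinib patients were treated for 13.9 months or less. The 35% is described through mood, speech and cognitive effects and the 42% simply as CNS events, so part of the rise may be definitional. All of this stands, and it leaves the gap unquantified.

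**Stronger readings that the documents do not support:**

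- A reader might infer from section 9.9 that the protocol admits it cannot support this test. The disclaimer concerns association between an event and the drug, which is a different hypothesis from incidence against 42%.
- A reader might infer that true power is far below 80%, by discounting the 55% for shorter exposure or by treating CROWN as a second sample. The first has no basis in the documents, and it misleads if the null is left at its 5-year value. The second is a comparison that nobody planned.
- A reader might take the remark about under-detection as working against observing 55%. It can equally mean that recorded rates understate the true one, and the study asks patients about CNS symptoms through PRO-CTCAE.

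**Conclusion.** The point holds in two parts.

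The mismatch between section 9.5 and section 9.7 is plain from the text and needs no assumption. The study is sized by a test that the protocol does not plan. The size itself is sound: given alpha 0.05, 116 provides 78.9% exact power for a one-sample test, and it supports an estimate to within about 9 percentage points whether or not a test is run.

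The difference in observation time is also established, at 12 to 30 months here against a 5-year report, and section 9.5 does not mention it. Other things equal, it can only lower the observed percentage relative to 42%. By how much cannot be derived from the protocol. No decision rule is attached to the 42%, so the harm is one of interpretation.

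This should be corrected, but it does not threaten the feasibility or size of the study.

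**What to change.** 1. In the abstract and sections 9.1, 9.2 and 9.5, replace the power sentence with one on precision, for example: *116 patients give a 95% CI half-width of about 9 percentage points for a CNS AE incidence of 42–55%.* If a test is wanted after all, state its null value, alpha and time window, and add it to section 9.7.
2. Beside the crude percentage, report first any-grade CNS adverse event as cumulative incidence at 12 and 18 months from first dose, with death as a competing event and 95% CIs. Time to onset of adverse events is already among the variables in section 9.3.
3. Quote the CROWN rates descriptively and with their follow-up: 35% at 3 years, 42% in the 5-year report.

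The cost is a wording change in the protocol and a modest amount of extra analysis. The sponsor gives up a formal power claim if it takes the precision route. The sample size, visits and data capture are unchanged.

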9.6. Data Management

The investigator will collect data from the enrolled patients in an electronic Case Report Form specially designed for this study.

The patient number we provide is a serial number devoid of any identifying value.

The information is stored in an Access database, which in turn is associated with a file, "WorkGroup", detailing the user code and permits of the investigator within the database. People not within this working group cannot access the database.

A Data Management Plan (DMP) will be developed and once approved by the person responsible for the study, the "Queries" will be programmed in the electronic case form so that when the investigator saves the data, it informs him/her of any doubts regarding the data.

All changes made by the investigators during the collection of data will be stored in a table specially designed for this function indicating the user, date, modified field, the old value and the new value.

9.6.1. Case Report Forms (CRFs)/Data Collection Tools (DCTs)/Electronic Data Record

As used in this protocol, the term CRF should be understood to refer to either a paper form or an electronic data record or both, depending on the data collection method used in this study.

A CRF is required and should be completed for each included patient. The completed original CRFs are the sole property of Pfizer and should not be made available in any form to third parties, except for authorized representatives of Pfizer or appropriate regulatory authorities, without written permission from Pfizer. The investigator shall ensure that the CRFs are securely stored at the study site in encrypted electronic form and will be password protected to prevent access by unauthorized third parties.

The investigator has ultimate responsibility for the collection and reporting of all clinical, safety, and laboratory data entered on the CRFs and any other data collection forms (source documents) and ensuring that they are accurate, authentic/original, attributable, complete, consistent, legible, timely (contemporaneous), enduring, and available when required. The CRFs must be signed by the investigator or by an authorized staff member to attest that the data contained on the CRFs are true. Any corrections to entries made in the CRFs or source documents must be dated, initialed, and explained (if necessary) and should not obscure the original entry.

In most cases the source documents are the hospital or the physician's chart. In these cases, data collected on the CRFs must match those charts.

In some cases, the CRF may also serve as the source document. In these cases, a document should be available at the investigator site and at Pfizer that clearly identifies those data that will be recorded on the CRF, and for which the CRF will stand as the source document.

The study variables will be recorded in an electronic case report form (eCRF) specially designed for the study. Answers of patients to the questionnaires and items will be collected through a tablet and the informed consent to participate in the study will be also collected in paper.

